Summaries of the number and percentage of participants with these events will be provided for each type of events separately by preferred term and maximum grade. The time to onset and duration of first occurrence for each type of events will be summarized using summary statistics mean, standard deviation, median, minimum value, and maximum. The number and percentage of participants who have time to onset of first occurrence in categories of (1-21, 22-42, 43-63, >63 days) will be reported for corneal events (CTCAE) and thrombocytopenia. The number and percentage of participants who have time to onset of first occurrence in categories of (0-6, >6-12, >12-18, >18-24, >24 hours) will be reported for infusion-related reactions. The number and percentage of participants who have duration of first occurrence in categories of (1-21, 22-42, 43-63, 64-84, 85-105, >105 days) will be reported for corneal events (CTCAE) and thrombocytopenia. The number and percentage of participants who have duration of first occurrence in categories of (0-12, >12-24, >24 hours) will be reported for infusion-related reactions. For an AESI which is based on a single adverse event term, the onset and duration will be calculated based on the start and end dates of the single term. For an AESI which is based on multiple adverse event terms, the onset and duration will be calculated by looking across all terms for the AESIs. The derived start date is identified as the onset of any term defined as the AESI. The derived end date is identified as last end date for any terms once all concurrent terms for the AESI have resolved, i.e., the first time a subject is free of any adverse event term defined as the AESI.

The summary of event characteristics will be provided for each AESI respectively, including number of participants with any event, number of events, number of participants with any event that is serious, number of participants with any event that is related to study intervention, number of occurrences (One, Two, Three or more), maximum grade, maximum grade for events related to study intervention, outcomes and the action taken for the event. The percentage will be calculated in two ways, one with number of participants with event as the denominator and the other with total number of participants as the denominator. The worst-case approach will be applied at participant

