- Shift table from baseline to worst case post-baseline by eye (R/L) for corneal epithelium findings:
  - Corneal epithelium (Normal to Abnormal),
  - Microcyst-like deposits (No to Yes).
  - Subepithelial haze (No to Yes)
  - Stromal opacity (No to Yes)
  - Epithelial edema (No to Yes)
  - Corneal epithelia defect (No to Yes)
  - Corneal erosion (No to Yes)
  - Corneal ulcer (No to Yes)
  - Corneal neovascularization (No to Yes)
  - Superficial punctate keratopathy severity (No to yes)
  - Stippled peripheral corneal staining  $\pm$  vortex/whorl staining pattern (No to Yes), summarize only for patients enrolled under protocol amendment 1.

iii. Lens

- Shift table from baseline to worst case post-baseline by eye (R/L) for lens findings:
  - Cataract (No to Yes)

Supportive listings may be provided, e.g.

- Listing of participants which fall into each of the two categories of change from baseline in BCVA: “possible worsened vision”, “definite worsened vision” with sub-categories “increase  $\geq 0.3$  to  $< 0.6$ ”, and “increase  $\geq 0.6$ ”.
- Listing of participants who fall into each of the two categories of decline in BCVA to ‘light perception’ (LP) or ‘no light perception’ (NLP) anytime post-baseline.
- Listings of participants with cataracts at baseline, pseudophakia at Baseline, who developed cataracts post-baseline, and who underwent cataract surgery post-baseline will be provided.
- Listing of impact on driving and reading if data are available
- Listing of corneal exam results

Details of the displays are to be provided in Output and Programming Specification document.

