#### 4.5.3.2. Corneal Events Based on Keratopathy and Visual Acuity Scale (KVA Scale)

For ocular exam visits based on the ocular worksheet under the original protocol, KVA grade is not expected to be collected. For ocular exam visits based on the ocular worksheet under the protocol amendment 1, KVA grade is expected to be collected. Analyses in this section will be based on collected / investigator reported KVA scale only.

Unless otherwise specified, for the following analyses, corneal events (KVA scale) will be summarized by treatment arms based at subject level (subject level KVA grade at each visit is defined as worse-eye grade at each visit).

An overview summary of corneal events (KVA scale) will be provided, including numbers and percentages of participants with any corneal events (KVA scale), and corneal events Grade 2 or above and Grade 3 or above (KVA scale).

In addition to the overview summary described above, an additional overview summary of corneal events (KVA scale) will be provided for only those participants enrolled under protocol amendment 1, including numbers and percentages of participants with any corneal events (KVA scale) leading to permanent discontinuation of study intervention, corneal events (KVA scale) leading to dose reductions, and corneal events (KVA scale) leading to dose delays.

A summary of characteristics of corneal events (KVA scale) of grade 2 or above by subject will be provided, including time to onset of first occurrence: summary statistics and frequency/percentage in categories (1-21, 22-42, 43-63, 64-105, >105 days); outcome of first occurrence, duration of first occurrence: summary statistics and frequency/percentage in categories (1-21, 22-42, 43-63, 64-105, >105 days); number of occurrences based on participants with corneal events (KVA scale) of grade 2 or above; outcome post treatment exposure; time to resolution post treatment exposure; outcome of last event. The duration is defined as time from onset of any corneal events (KVA scale) of grade 2 or above to the first time the subject is free of overall KVA grade  $\geq 2$ . It requires at least one day gap between the resolution of all events from first occurrence to the onset of second occurrence.

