A summary of characteristics of corneal exam findings (KVA scale) of grade 2 or above by subject will be provided, including time to onset of first occurrence: summary statistics and frequency/percentage in categories (1-21, 22-42, 43-63, 64-105, >105 days); outcome of first occurrence, duration of first occurrence: summary statistics and frequency/percentage in categories (1-21, 22-42, 43-63, 64-105, >105 days); number of occurrences based on participants with corneal exam findings (KVA scale) of grade 2 or above; outcome post treatment exposure; time to resolution post treatment exposure; outcome of last event. The duration is defined as time from onset of any corneal exam findings (KVA scale) of grade 2 or above to the first time the subject is free of any corneal exam findings with KVA scale grade  $\geq 2$ . It requires at least one day gap between the resolution of all events from first occurrence to the onset of second occurrence.

A summary of characteristics of visual acuity (KVA scale) of grade 2 or above by subject will be provided, including time to onset of first occurrence: summary statistics and

frequency/percentage in categories (1-21, 22-42, 43-63, 64-105, >105 days); outcome of first occurrence, duration of first occurrence: summary statistics and frequency/percentage in categories (1-21, 22-42, 43-63, 64-105, >105 days); number of occurrences based on participants with visual acuity (KVA scale) of grade 2 or above; outcome post treatment exposure; time to resolution post treatment exposure; outcome of last event. The duration is defined as time from onset of any visual acuity (KVA scale) of grade 2 or above to the first time the subject is free of visual acuity with KVA scale grade  $\geq 2$ . It requires at least one day gap between the resolution of all events from first occurrence to the onset of second occurrence.

For the summary of characteristics tables above, the end of treatment exposure is defined as last infusion date +20 days for belantamab Mafodotin arm; the end of treatment exposure is defined as overall study treatment end date (i.e. the end date of last cycle) for Pom/Dex arm as defined in Section 4.5.1.

A summary of corneal events (KVA scale) by grade and visit will be provided, worst-case post-baseline overall KVA grade will also be provided.

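### In the by-eye corneal shift table, the row for superficial punctate keratopathy severity shifts only presence or absence, so worsening in an already affected eye shows there as no change

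*SAP*

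**What the plan says.** SAP section 4.5.3.1, part ii (Corneal Exam), plans a "Shift table from baseline to worst case post-baseline by eye (R/L) for corneal epithelium findings". Eleven rows follow. The first, on the state of the corneal epithelium, shifts from Normal to Abnormal. The other ten shift from No to Yes. Nine of those ten are named as findings that are either there or not, for example "Microcyst-like deposits (No to Yes". The remaining one is "Superficial punctate keratopathy severity (No to yes". It is the only row whose name refers to severity.

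The SAP lists no severity levels for this finding and plans no graded shift for it in any other section. The part on supportive listings includes one of corneal exam results, under the lead-in "Supportive listings may be provided, e.g". Display details are left to the Output and Programming Specification (OPS).

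Two other sections carry graded corneal information:

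- Section 4.5.3.2 summarizes the KVA scale, with the caveat "For ocular exam visits based on the ocular worksheet under the original protocol, KVA grade is not expected to be collected".
- Section 4.5.2.1 summarizes corneal events graded by CTCAE, "separately by preferred term and maximum grade".

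**The concern.** A severity cannot be answered No or Yes, so the row's name and its categories do not fit together. If the table is programmed as written, it can show new onset of the finding and nothing else. It cannot show that an eye with some keratopathy at baseline became worse on treatment, nor how severe keratopathy became in an eye that was clear at baseline.

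Ocular findings on ophthalmic exam are a named secondary safety endpoint (section 1.1.1), and corneal events are an adverse event of special interest (section 4.5.2.1). This row is the only planned summary built on this exam finding by eye and relative to the baseline exam. At stake is how fully one safety finding is described. No hypothesis test is involved.

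**Working it through.** The SAP has no figure to reproduce here. The check is to work through the table and then set it beside the other planned displays.

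**Step 1: what a two-level shift can show.** Suppose the worksheet records none plus k severity levels; k is not in the SAP. Baseline by worst later value then gives (k + 1)² possible pairs, and the No/Yes table folds them into four cells. Taking Yes to mean any keratopathy:

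| Cell | Pairs in it | What it mixes |
|---|---|---|
| No/No | 1 | nothing |
| No/Yes | k | new onset at every severity |
| Yes/No | k | clearance from every severity |
| Yes/Yes | k² | k stable pairs, k(k − 1)/2 worsened pairs, k(k − 1)/2 improved pairs |

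The pairs add up: 1 + k + k + k² = (k + 1)². With k = 1, which is presence only, k(k − 1)/2 = 0 and nothing is lost. With k = 2, the smallest graded case, Yes/Yes holds 4 pairs: 2 stable, 1 worsened and 1 improved. So as soon as there are two severity levels, a worsened eye shares a cell with stable eyes and two severities of new onset cannot be told apart. If Yes instead means above some threshold, the SAP does not state the threshold.

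**Step 2: does another display supply the missing information?**

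| Display | Unit | Specific to this exam finding? | Shift from the baseline exam? | Coverage |
|---|---|---|---|---|
| Shift row, 4.5.3.1 ii | eye | yes | yes, two levels only | no worksheet limit stated for this row |
| KVA summaries, 4.5.3.2 | participant (worse eye) | no, scale-level grade | no | not expected for visits on the original-protocol worksheet |
| CTCAE corneal events, 4.5.2.1 | participant | no, reported events by preferred term | no | no worksheet restriction stated |
| Listing of corneal exam results, 4.5.3.1 | participant listing | potentially | no | optional |

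None of the last three is a graded, by-eye shift for this finding.

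**Step 3: how does the SAP treat other graded safety data?** In part i of the same section, visual acuity change is divided into bands with cut-points at 0.12, 0.3 and 0.6 logMAR. Section 4.5.4.1 summarizes increases from baseline grade for gradable laboratory tests. Section 4.5.4.2 does the same for blood pressure, with separate counts for increases to Grade 2 and to Grade 3. A two-level shift for an item named as a severity departs from that practice, and no reason is given.

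**The case against.** The strongest reply is that graded corneal severity is planned, and in some detail. Section 4.5.3.2 counts participants at KVA Grade 2 or above and Grade 3 or above. It describes the corneal-exam component separately from the visual-acuity component (onset, duration, recurrence and outcome at grade 2 or above), tabulates grade by visit, and adds that "worst-case post-baseline overall KVA grade will also be provided". Section 4.5.2.1 adds CTCAE corneal events by maximum grade. All of this stands. A reader might infer from the shift row that the trial will not report how severe corneal toxicity was. The SAP does not support that, because the limitation belongs to one table.

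A second reply concerns the data. A reader might infer that recorded severity is being thrown away. The only evidence that levels are recorded is the word in the row label. The worksheet and the OPS are not at hand, and the label could be a slip in a list of present/absent findings. That also stands, and the fix must cover both possibilities.

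Third, the KVA gap on the old worksheet may be small. The limit is worded by visit, the SAP gives no share of visits affected, and the first KVA overview is not restricted to participants enrolled under protocol amendment 1. It would therefore be wrong to infer that those enrolled earlier have no graded corneal data.

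Finally, display details are deferred to the OPS, which could add levels. But the SAP itself states the No/Yes categories, and an OPS that follows it would repeat them.

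**Conclusion.** The point holds for this table. As written, a severity-named row shifts only presence or absence. Worsening in an eye already affected at baseline appears there as no change, and the severity of new-onset keratopathy is not shown. The KVA and CTCAE summaries partly mitigate this but are not by-eye shifts of this finding from the baseline exam.

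The loss occurs only if the worksheet records at least two severity levels, which the label suggests but the SAP does not confirm. If it records presence only, nothing is lost and the label alone is wrong. Either way, label and categories need reconciling.

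No proportion of eyes can be put on the effect, because the SAP gives neither how common the finding is at baseline nor how often it worsens. The effect is limited to one row of a descriptive safety display. Estimands, error rates and efficacy results are untouched, so this is a free improvement rather than a defect that threatens a conclusion.

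**What to change.** In section 4.5.3.1 ii, replace the row with a by-eye shift across none and each severity level recorded on the ocular worksheet, from the baseline exam to the worst later exam. Add a row counting eyes with any increase in severity. Keep No to Yes for the findings that are purely present or absent. If the worksheet turns out to record presence only, delete the word severity from the label instead.

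The cost is one table shell and the matching line in the OPS. If levels are recorded, no new data or procedure is needed; if they are not, only the label changes.

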#### 4.5.3.2. Corneal Events Based on Keratopathy and Visual Acuity Scale (KVA Scale)

For ocular exam visits based on the ocular worksheet under the original protocol, KVA grade is not expected to be collected. For ocular exam visits based on the ocular worksheet under the protocol amendment 1, KVA grade is expected to be collected. Analyses in this section will be based on collected / investigator reported KVA scale only.

Unless otherwise specified, for the following analyses, corneal events (KVA scale) will be summarized by treatment arms based at subject level (subject level KVA grade at each visit is defined as worse-eye grade at each visit).

An overview summary of corneal events (KVA scale) will be provided, including numbers and percentages of participants with any corneal events (KVA scale), and corneal events Grade 2 or above and Grade 3 or above (KVA scale).

In addition to the overview summary described above, an additional overview summary of corneal events (KVA scale) will be provided for only those participants enrolled under protocol amendment 1, including numbers and percentages of participants with any corneal events (KVA scale) leading to permanent discontinuation of study intervention, corneal events (KVA scale) leading to dose reductions, and corneal events (KVA scale) leading to dose delays.

A summary of characteristics of corneal events (KVA scale) of grade 2 or above by subject will be provided, including time to onset of first occurrence: summary statistics and frequency/percentage in categories (1-21, 22-42, 43-63, 64-105, >105 days); outcome of first occurrence, duration of first occurrence: summary statistics and frequency/percentage in categories (1-21, 22-42, 43-63, 64-105, >105 days); number of occurrences based on participants with corneal events (KVA scale) of grade 2 or above; outcome post treatment exposure; time to resolution post treatment exposure; outcome of last event. The duration is defined as time from onset of any corneal events (KVA scale) of grade 2 or above to the first time the subject is free of overall KVA grade  $\geq 2$ . It requires at least one day gap between the resolution of all events from first occurrence to the onset of second occurrence.

A summary of characteristics of corneal exam findings (KVA scale) of grade 2 or above by subject will be provided, including time to onset of first occurrence: summary statistics and frequency/percentage in categories (1-21, 22-42, 43-63, 64-105, >105 days); outcome of first occurrence, duration of first occurrence: summary statistics and frequency/percentage in categories (1-21, 22-42, 43-63, 64-105, >105 days); number of occurrences based on participants with corneal exam findings (KVA scale) of grade 2 or above; outcome post treatment exposure; time to resolution post treatment exposure; outcome of last event. The duration is defined as time from onset of any corneal exam findings (KVA scale) of grade 2 or above to the first time the subject is free of any corneal exam findings with KVA scale grade  $\geq 2$ . It requires at least one day gap between the resolution of all events from first occurrence to the onset of second occurrence.

A summary of characteristics of visual acuity (KVA scale) of grade 2 or above by subject will be provided, including time to onset of first occurrence: summary statistics and

frequency/percentage in categories (1-21, 22-42, 43-63, 64-105, >105 days); outcome of first occurrence, duration of first occurrence: summary statistics and frequency/percentage in categories (1-21, 22-42, 43-63, 64-105, >105 days); number of occurrences based on participants with visual acuity (KVA scale) of grade 2 or above; outcome post treatment exposure; time to resolution post treatment exposure; outcome of last event. The duration is defined as time from onset of any visual acuity (KVA scale) of grade 2 or above to the first time the subject is free of visual acuity with KVA scale grade  $\geq 2$ . It requires at least one day gap between the resolution of all events from first occurrence to the onset of second occurrence.

For the summary of characteristics tables above, the end of treatment exposure is defined as last infusion date +20 days for belantamab Mafodotin arm; the end of treatment exposure is defined as overall study treatment end date (i.e. the end date of last cycle) for Pom/Dex arm as defined in Section 4.5.1.

A summary of corneal events (KVA scale) by grade and visit will be provided, worst-case post-baseline overall KVA grade will also be provided.

A summary of first dose delay due to corneal events (KVA Scale) will be provided for patients enrolled under protocol amendment 1 and belantamab mafodotin arm only, since under the original protocol, KVA scale is not used as guidance for dose modification. The table includes number of participants with dose delay due to corneal events (KVA Scale), grade of corneal events (KVA Scale) at onset of the dose delay; maximum grade of corneal events (KVA Scale) during the first dose delay; grade of corneal events (KVA Scale) at restart following the first dose delay; duration of first dose delay; frequency and percentage of whether dose is reduced at restart. The onset of dose delay is defined as previous dose date + 21 days (cycle length) + 3 days (visit window).

Details of the displays are to be provided in Output and Programming Specification document.

#### **4.5.4. Additional Safety Assessments (if applicable)**

##### **4.5.4.1. Laboratory Data**

Laboratory evaluations including the analyses of Chemistry laboratory tests, Haematology laboratory tests, Urinalysis, and liver function tests will be based on GSK Core Data Standards.

Summary of change from baseline by scheduled visits using mean, median, standard deviation, minimum and maximum will be provided.

Summaries of worst case grade increase from baseline grade will be provided for all the lab tests that are gradable by CTCAE v5.0. These summaries will display the number and percentage of participants with a maximum post-baseline grade increasing from their baseline grade. Any increase in grade from baseline will be summarized along with any increase to a maximum grade of 3 and any increase to a maximum grade of 4. Missing baseline grade will be assumed as grade 0. For laboratory tests that are graded for both low and high values, summaries will be done separately and labelled by direction, e.g., sodium will be summarized as hyponatremia and hypernatremia separately.

For lab tests that are not gradable by CTCAE v5.0, summaries of worst case changes from baseline with respect to normal range will be generated. Decreases to low, changes to normal or no changes from baseline, and increases to high will be summarized for the

worst case post-baseline. If a subject has a decrease to low and an increase to high during the same time interval, then the subject is counted in both the “Decrease to Low” categories and the “Increase to High” categories.

Separate summary tables for haematology, and chemistry laboratory tests will be produced. Liver function laboratory tests will be included with chemistry lab tests.

For spot urine albumin/creatinine ratio (mg/g), a shift table from baseline to worst post-baseline will be provided.

A supporting listing of laboratory data for participants with abnormalities of potential clinical concern will be provided. A separate listing of laboratory data with character values will also be provided.

Unless otherwise specified, the denominator in percentage calculation at each scheduled visit will be based on the number of participants with non-missing value at each particular visit.

Summaries of hepatobiliary laboratory events including possible Hy’s law cases will be provided in addition to what has been described above. Possible Hy’s law cases are defined as any elevated alanine aminotransferase (ALT) $>3\times$ upper limit of normal (ULN), total bilirubin $\geq 2\times$ ULN and alkaline phosphatase (ALP) $<3\times$ ULN/missing. Total bilirubin $\geq 2\times$ ULN can be within 28 days following the ALT elevation and if direct bilirubin is available on the same day, it must be  $\geq 35\%$  of total bilirubin.

ALP $<3\times$ ULN/missing means it is satisfied unless the ALP is  $\geq 3\times$ ULN at the time of bilirubin elevation. The summary will be produced for worst case post baseline only.

An e-DISH plot of maximum post baseline total bilirubin versus maximum post baseline ALT will be created.

The following plots will also be provided:

- maximum post baseline ALT versus baseline ALT
- maximum post baseline AST versus maximum post baseline LDH
- maximum post baseline AST versus maximum post baseline Creatinine Kinase
- maximum post baseline LDH versus maximum post baseline Creatinine Kinase

maximum post baseline urine albumin versus maximum post baseline urine CreatinineA summary of Liver Monitoring/Stopping Event Reporting will be provided. The medical conditions data for participants with liver stopping events will be listed. The substance use data for participants with liver stopping events will be listed.

